## 1.3 Outcomes, Exposures, and Additional Variables of Interest

### 1.3.1 Maneuver Variables

Maneuver	Variable(s)	Description	Specifications

A	dprs_servo[1-5]	Static Respiratory System Driving Pressure from Ventilator	Calculated within REDCap as: pplat_servo_a[1-5] - peep_vent_a[1-5]
B	p0_1_[1-5]	P 0.1 from Servo	Entered directly into REDCap
C	paw_max_b[1-5]	Max Airway Pressure	Entered directly into REDCap
	peep_vent_b[1-5]	PEEP from Ventilator	Entered directly into REDCap
	aop_[1-5]	Airway Occlusion Pressure	Calculated within REDCap as: peep_vent_c[1-5] - max_neg_paw[1-5]
	pred_delta_pl_[1-5]	Predicted $\Delta P_L$	Calculated as: paw_max_b[1-5] - peep_vent_b[1-5] + (2/3)*aop_[1-5]
D	dprs_stat_vc_d[1-5]	Static Respiratory System Driving Pressure	Calculated within REDCap as: pplat_aw_d[1-5] - peep_vent_d[1-5]

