### 1.4.3 Analyses Plan for Aim 2

For each pair of maneuvers, the consistency of the measures between the two methods will be quantified using the interclass correlation coefficient  $\rho_{inter}$ .

$\rho_{inter}$  gives the correlation between any two measurements from the same patients from different methods.

Similarly to Aim 1, the  $\rho_{inter}$  is defined as

$$\rho_{inter} = \frac{\sigma_\alpha^2}{\sigma_\alpha^2 + \sigma_\gamma^2 + \sigma_\epsilon^2}$$

95% confidence intervals for each of the variances, as well as the ICC, will be calculated using the empirical 2.5th and 97.5th percentiles of 10,000 parametric bootstrap replications.

For each maneuver, the within-subject mean values will be calculated. For each pair of maneuvers (A and B, A and C, etc) the subject-level mean values will be plotted.

Summaries of the subject-level mean and standard deviations will be reported using mean with standard deviation, median with first and third quartiles, and range, stratified by maneuver.

Technical details:

The values for  $\sigma_\alpha^2, \sigma_\gamma^2, \sigma_\epsilon^2$  are estimated from the linear mixed effects-model

$$Y_{ijk} = \mu + \alpha_i + \beta_j + \gamma_{ij} + \epsilon_{ijk}$$

Where  $Y_{ijk}$  is the  $k$ th measurement coming from the  $i$ th patient using method  $j$ .

Here,  $i$  indexes the 15 patients,  $j$  indexes the either the first or second of the two methods (A or B, A or C, etc), and  $k$  indexes the breath number for patient  $i$  on method  $j$ . Because some measurements were discarded, each patient on each method has up to, but sometimes less than, 5 repetitions.

The various terms represent:

- $\mu$  = the overall mean value for method 1
- $\alpha_i$  = the subject-specific deviation from the overall mean for method 1
- $\mu + \alpha_i$  = the subject-specific mean for method 1
- $\beta_j$  = the deviation in the overall mean for method 2 from method 1
- $\mu + \beta_j$  = the overall mean for method 2
- $\gamma_{ij}$  = the subject-specific interaction term for method 2 (relative to the subject-specific deviation for method 1)
- $\alpha_i + \gamma_{ij}$  = the subject-specific deviation from the overall mean for method 2

We assume that

$$\alpha_i \sim N(0, \sigma_\alpha^2), \quad \gamma_{ij} \sim N(0, \sigma_\alpha^2), \quad \epsilon_{ijk} \sim N(0, \sigma_\epsilon^2)$$

With  $\alpha_i$ ,  $\gamma_{ij}$ , and  $\epsilon_{ijk}$  each iid and mutually independent of each other.

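### SAP 1.4.3: the Aim 2 term list and distribution line do not match the formula for ρ_inter

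*SAP*

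**What the plan says.** All of this is in SAP 1.4.3 (Aim 2).

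- **Meaning of ρ_inter.** It "gives the correlation between any two measurements from the same patients from different methods".
- **Formula.** The patient variance σ_α² is divided by the sum σ_α² + σ_γ² + σ_ε². The technical details say that these three variances "are estimated from the linear mixed effects-model" with terms μ, α_i, β_j, γ_ij and ε_ijk.
- **Term list.** α_i is "the subject-specific deviation from the overall mean for method 1", and μ + α_i is the patient's mean on method 1. γ_ij is "the subject-specific interaction term for method 2 (relative to the subject-specific deviation for method 1"), and α_i + γ_ij is the patient's deviation on method 2.
- **Distribution line.** "\gamma_{ij} \sim N(0, \sigma_\alpha^2"), so γ_ij has the patient variance and σ_γ² is attached to no term. The next line calls the γ_ij iid.
- **Intervals.** The section promises "confidence intervals for each of the variances, as well as the ICC", from 10,000 parametric bootstrap replications.

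The statistic is computed for all six pairs of maneuvers. SAP 1.3.1 shows that they are not all the same quantity: A and D are driving pressures, B is "P 0.1 from Servo", and C is a predicted change in lung pressure.

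**The concern.** The section describes more than one model. The formula belongs to a model in which both methods carry their own γ_ij. The term list describes one in which method 1 has none. The distribution line describes a third, in which γ_ij has the same variance as α_i.

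ρ_inter and its interval are the main Aim 2 result. If the term list was coded and the printed formula applied, the reported number is not the correlation that the SAP says it is, and it can change when the two maneuvers swap labels. A between-method coefficient should not do that. A parametric bootstrap simulates from the fitted model, so the intervals inherit the same error.

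**Working it through.** Write a, g and e for σ_α², σ_γ² and σ_ε². The SAP gives no values for them, so every number below rests on assumed variances. The 15 patients and up to 5 breaths per method come from SAP 1.4.3.

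**1. γ_ij for both methods, own variance.** Each method has variance a + g + e, and the covariance between methods is a. The correlation is a/(a + g + e), which is the printed formula.

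**2. Term list as written, γ_ij for method 2 only.** Method 1 has variance a + e, method 2 has a + g + e, and the covariance is a. The correlation is a/√[(a + e)(a + g + e)]. The printed formula equals this multiplied by √[(a + e)/(a + g + e)], so it is too low whenever g > 0.

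- (a, g, e) = (9, 4, 1): formula 9/14 = 0.643; model's correlation 9/√(10 × 14) = 0.761.
- (9, 1, 1): formula 9/11 = 0.818; model's correlation 9/√(10 × 11) = 0.858.

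**3. Distribution line as written, g = a, for both methods.** ρ_inter becomes a/(2a + e), which cannot exceed 0.5. For a truth of (9, 1, 1) with 5 breaths per method, the expected mean squares are 10 × 9 + 5 × 1 + 1 = 96 (patients, 14 df), 5 × 1 + 1 = 6 (patient by method, 14 df) and 1 (breaths, 120 df). A REML fit to these under g = a gives 0.441 against the true 9/11 = 0.818.

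**4. Label order under the term-list model.** This model forces method 2 to vary at least as much between patients as method 1. It was fitted by maximum likelihood to the population covariance, with breath SD 1 and 5 breaths per method, and the printed formula was then applied. For patient-level SDs s1 and s2 and correlation r, the true correlation of single measurements is r·s1·s2/√[(s1² + 1)(s2² + 1)]. For SDs 3 and 1.5 and r = 0.9 it is 4.05/√(10 × 3.25) = 0.710.

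| Patient SDs, r | Wider method first | Wider method second | Both-methods model | True |
|---|---|---|---|---|
| 3 and 1.5, 0.9 | 0.682 | 0.356 | 0.611 | 0.710 |
| 3 and 2.5, 0.9 | 0.764 | 0.695 | 0.783 | 0.793 |
| 3 and 3, 0.9 | 0.762 | 0.762 | 0.810 | 0.810 |
| 3 and 1.5, 0.5 | 0.536 | 0.225 | 0.340 | 0.395 |

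In the last row the term-list value is above the truth in one order and below it in the other, so the direction of the error is not fixed.

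**5. Samples of the planned size.** In 600 simulated data sets of 15 patients, 2 methods and 5 breaths, fitted by REML, swapping the labels moved the estimate by a median of 0.32 (SDs 3 and 1.5, r = 0.9). With equal true variances (9, 4, 1) the median was 0.06 and the 90th percentile 0.16.

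**The case against.** The strongest reply is that this is a wording fault in a specification that is otherwise coherent. The model equation, the iid line, the formula and the verbal definition all fit the usual model with a patient effect and a patient-by-method effect. A standard patient-by-method random term gives the printed formula exactly. σ_γ² is named twice elsewhere in the section, so the subscript in the distribution line is probably a slip, and coding it literally would be odd. That is fair, and the 0.44 figure should be read with that in mind.

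The term list does not depend on that subscript. Several of its entries consistently tie α_i to method 1 and γ_ij to method 2. A random intercept plus an uncorrelated random effect for a method 2 indicator would be a direct coding of it, and nothing in the documents excludes this.

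Two further points stand. First, the largest label effects need unequal between-patient variances, and the both-methods model assumes equal variances too. For SDs 3 and 1.5 with r = 0.9 it gives 0.61, which is further from the true 0.71 than the term-list model with the wider method first (0.68). The correction removes the dependence on labels but not this bias. Second, with equal variances the median label effect of 0.06 is small beside the sampling SD of ρ_inter, about 0.15 with 15 patients at (9, 4, 1).

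The study is descriptive and no decision rule is attached to ρ_inter. That limits the consequences, but it also makes the estimate and its interval the result itself.

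**Conclusion.** The concern holds. The term list and the distribution line in SAP 1.4.3 each contradict the formula for ρ_inter, and the algebra shows this without any assumed value. The size does depend on assumptions:

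- For the two variance sets in step 2, the formula understates the term-list model's own correlation by 0.04 to 0.12.
- Label order makes no difference in the population when the between-patient variances are equal, and a difference of 0.33 (0.682 − 0.356) when the SDs are 3 and 1.5 with r = 0.9. Equal variances cannot be taken for granted when P0.1 is paired with driving pressures.

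If the code already uses a patient-by-method term for both methods, no result changes and only the text is wrong. The documents do not settle which was coded. This should be fixed.

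**What to change.** In SAP 1.4.3:

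1. State γ_ij ~ N(0, σ_γ²), independent for j = 1 and j = 2.
2. Define α_i as the patient effect shared by both methods, and μ + β_j + α_i + γ_ij as the patient's mean on method j for both methods.
3. Confirm that the fitted random-effects code and the parametric bootstrap use this model.

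The printed formula is then the model's between-method correlation and does not depend on labels. If the method-2-only model was intended, the formula must change instead to σ_α²/√[(σ_α² + σ_ε²)(σ_α² + σ_γ² + σ_ε²)]. The SAP would then also have to say which maneuver is method 1 in each pair and why. The first route is preferable because it has no label dependence.

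As an optional sensitivity analysis, fit method-specific variances, since the corrected model still assumes them equal.

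The cost is a few lines of text and one check of the code and bootstrap. The optional analysis adds variance parameters that will be less precise with 15 patients.

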#### 1.4.4 Bland-Altman Plot

A Bland-Altman (Tukey mean-difference) plot will be created for maneuvers A and D.

This plot will show the difference between measurements on the y-axis, and the average of measurements on the x-axis. 95% limits of agreement are calculated for the difference between measurements (y-axis) values by calculating the usual 95% confidence interval for the mean of the differences (that is, roughly, [mean of differences]  $\pm$  1.96 \* [standard deviation of the differences]).
